**Figure 5: RAIN-3201 Study Design Diagram**

BICR = blinded independent central review; DCR = disease control rate; DD = dedifferentiated; DOR = duration of response; EU = European Union; HRQoL = health-related quality of life; ORR = objective response rate; OS = overall survival; PFS = progression-free survival; RECIST = Response Evaluation Criteria in Solid Tumors; TP53 = tumor protein p53; WD = well-differentiated

## 4.2 Imaging Assessments by Blinded Independent Central Review

### 4.2.1 Intensive Electrocardiogram and Pharmacokinetics Evaluation in a Subgroup of Milademetan-Treated Patients

## **4.3 Endpoints and Criteria for Evaluation**

### **4.3.1 Primary Endpoint**

The primary efficacy endpoint is PFS defined as the time from randomization to the earliest date of the first objective documentation of radiographic disease progression as determined by BICR or death due to any cause. Tumor response will be assessed in accordance with RECIST version 1.1.

### **4.3.2 Secondary Endpoints**

Secondary efficacy endpoints include:

[figure not shown]
- OS as measured from the date of randomization to the date of death by any cause
- DCR defined as the percentage of patients who have achieved CR, PR, or SD for  $\geq 16$  weeks by BICR and Investigator assessment
- ORR defined as the percentage of patients who achieve a confirmed CR or PR by BICR and Investigator assessment
- DOR defined as the time from date of first response to date of disease progression or death by BICR and Investigator assessment
- PFS defined as the time from randomization to the earliest date of the first objective documentation of radiographic disease progression or death due to any cause, based on Investigator assessments

Health-related quality of life (HRQoL) endpoints include:

- European Organisation for Research and Treatment of Cancer (EORTC) Quality of Life Questionnaire, Core 30 (QLQ-C30)

Safety endpoints include the incidence of treatment-emergent AEs (TEAEs) (including SAEs, TEAEs leading to discontinuation of study drug, and TEAEs leading to study withdrawal); changes in clinical laboratory parameters (hematology, serum chemistry, coagulation, and serum and urine pregnancy test), deaths, vital signs, and electrocardiogram (ECG) parameters (especially QT intervals); physical examination results (including ECOG performance status); and use of concomitant medications.

#### **4.3.3 Exploratory Endpoints**

#### **4.4 Measures Taken to Minimize/Avoid Bias**

If a patient withdraws from the study, the data (including tested and untested samples) collected to the point of withdrawal will remain part of the study database and will not be removed.

Response criteria are based on objective measurements as defined in RECIST version 1.1 by site radiologists. All responses will be source verified; copies of tumor assessment scans will be collected and provided for evaluation by BICR (Section 4.2).

Biometrics representatives from the Sponsor team and BICR will remain blinded throughout the conduct of the study and described in a separate trial integrity document.

#### **4.5 Duration of Study Treatment**

Patients will continue to receive study drug (i.e., either milademetan or trabectedin) until documented disease progression or unacceptable toxicity. See Section 6.5 for treatment beyond progression.

[figure not shown]
### **5. SELECTION AND WITHDRAWAL OF PATIENTS**

#### **5.1 Inclusion Criteria**

Each patient must meet all of the following criteria to be enrolled in the study:

1. Is a male or female patient  $\geq$  18 years old
2. Has a signed and dated informed consent form prior to the start of any study-specific qualification procedures

3. Has histologically confirmed WD/DD liposarcoma, by local pathologic review; central pathologic review will also be performed, but is not required for inclusion

4. Has documented advanced unresectable (i.e., where resection is deemed to cause unacceptable morbidity or mortality) and/or metastatic WD/DD liposarcoma

5.

6.

7. Has resolution of any clinically relevant toxic effects of prior chemotherapy, surgery, radiotherapy, or hormonal therapy

8. Has an ECOG performance status of 0 or 1

9. Has adequate bone marrow function, defined as:

- a. Platelet count  $\geq 100 \times 10^9/L$
- b. Hemoglobin  $\geq 9.0 \text{ g/dL}$
- c. Absolute neutrophil count  $\geq 1.5 \times 10^9/L$

10. Has adequate renal function, defined as creatinine clearance  $\geq 30 \text{ mL/min}$ , as calculated using the modified Cockcroft-Gault equation (or equivalent glomerular filtration rate calculated using the Chronic Kidney Disease Epidemiology Collaboration formula)

11. Has adequate hepatic function, defined as:

[figure not shown]
- a. Alanine aminotransferase and aspartate aminotransferase  $\leq 3 \times$  upper limit of normal (ULN) if no liver metastases are present;  $\leq 5 \times$  ULN if liver metastases are present
- b. Total bilirubin  $\leq 1.5 \times$  ULN. Patients with Gilbert's disease who have serum bilirubin level  $\leq 3 \times$  ULN, may be enrolled

12. Is willing and able to comply with the protocol requirements

[figure not shown]
13. Patients requiring anticoagulation medication should be on a stable regimen, defined as at least 4 weeks on the same dose

14. Patients requiring antihypertensive medication should be on a stable regimen, defined as at least 4 weeks on the same dose

15. If a woman of childbearing potential (WOCBP), must have a negative serum pregnancy test at screening and a negative urine pregnancy test on Cycle 1 Day 1 before receiving her first dose of study drug or within 72 hours of the first dose of study drug

16. If a male patient, is surgically sterile, willing to use a condom, or remain abstinent upon randomization through the Treatment Period and for 5 months after the final dose of study drug

## 5.2 Exclusion Criteria

A patient who meets any of the following criteria will not be eligible to participate in the study:

1. Has received prior treatment with any MDM2 inhibitor or trabectedin
2. Has other primary malignancies that have required systemic antineoplastic treatment within the previous 2 years, except for localized cancers that have apparently been cured (e.g., nonmelanoma skin cancer, superficial bladder cancer, or carcinoma in situ of the prostate, cervix, or breast) and will not interfere with the study outcomes
3. Has gastrointestinal conditions that could affect the absorption of milademetan, in the opinion of the Investigator
4. Has an uncontrolled infection within the last 7 days from randomization requiring IV antibiotics, antivirals, or antifungals
5. Has known HIV infection or active hepatitis B or C infection
6. Has untreated brain metastases

7. Has not met the minimum washout period before randomization, defined as:

- a. CYP3A4 strong inhibitor: 5 elimination half-lives of the inhibitor
- b. CYP3A strong or moderate inducers (e.g., St. John's wort and modafinil): 4 weeks
- c. Systemic anticancer therapy (chemotherapy; small molecules, including antibody drug therapy; retinoid therapy; or hormonal therapy) or investigational therapy: 3 weeks or 5 half-lives, whichever is shorter
- d. Immunotherapy with checkpoint inhibitor: 4 weeks

8. Has had major surgery  $\leq$  3 weeks from randomization
9. Has had curative-intent radiation therapy  $\leq$  4 weeks or palliative radiation therapy, defined as  $\leq$  30 Gy in  $\leq$  10 fractions (e.g., 20 Gy in 5 fractions or 8 Gy in 1 fraction)  $\leq$  2 weeks from randomization
10. Has uncontrolled or significant cardiovascular disease, including:
  - a. QTcF at rest, where the mean QTcF interval is  $>$  480 milliseconds (average of triplicate ECGs)
  - b. Myocardial infarction within 6 months prior to screening
  - c. Uncontrolled angina pectoris within 6 months prior to screening
  - d. New York Heart Association Class 3 or 4 congestive heart failure
  - e. Uncontrolled hypertension (resting systolic blood pressure  $>$  150 mmHg or diastolic blood pressure  $>$  100 mmHg)
11. Is a female who is pregnant or breastfeeding or intends to become pregnant during the study
12. Has a concomitant medical condition that would interfere with the assessment of efficacy or increase the risk of toxicity, in the opinion of the Investigator or Sponsor

### **5.3 Study Completion**

Patient study “completion” refers to completion of study procedures and follow-up assessments or the patient has died, is lost to follow-up, or withdrawn consent before end of study.

### **5.4 Patient Withdrawal Criteria**

All patients are free to discontinue study drug or withdraw from the study at any time. All patients wishing to discontinue from study drug or withdraw from the study will be queried to determine the reason for withdrawal while respecting the privacy of the patient. The reason a patient decided to withdraw from study drug will be recorded.

In the event of consent withdrawal, the Investigator should make every effort to ensure that the patient is followed for AEs for a minimum of 30 days after their last dose of study drug or until the initiation of a new anticancer treatment, whichever comes first, with documented patient agreement.

Patients will be discontinued from study drug if any of the following events occur:

- PD according to RECIST version 1.1 at any time during the study (unless approved by the Medical Monitor [See Section [6.5](#)])

- Clinical progression (e.g., symptomatic deterioration) not meeting the RECIST version 1.1 criterion for PD but considered by the Investigator to require withdrawal from study drug
- Patient is unable to tolerate dosing after 3 dose reductions (for the milademetan arm) or is unable to maintain treatment with trabectedin following the dose modification guidelines provided in the local package insert/label (for the trabectedin arm)
- Patient is unable to restart trabectedin after a dosing delay of > 3 weeks due to a persistent adverse reaction
- Significant deviation from the protocol or eligibility criteria. These patients may continue study drug following a discussion and agreement between the Investigator and the Medical Monitor and subsequent approval by the institutional review board (IRB) or independent ethics committee (IEC).
- Pregnancy
- Patient withdrawal of consent and/or election to discontinue study drug
- Termination of the study by the Sponsor
- Any other reason which, in the opinion of the Investigator, would justify removing the patient from the study drug

A patient may also be withdrawn from study drug by the Sponsor, Regulatory Authorities, or IECs/IRBs.

If a patient discontinues study drug due to the ongoing coronavirus disease 2019 (COVID-19) global pandemic, information should be captured in the electronic case report form (eCRF) so this information can be summarized in the clinical study report at the end of the study, in line with the FDA guidance ([FDA 2020](#)). The reason for discontinuation should be recorded in the eCRF as COVID-19, if applicable, and include as many details as possible. For example, specific reasons may include, but are not limited to:

- The patient exhibits symptoms consistent with COVID-19.
- The patient has a positive test result for COVID-19.
- The patient has neither symptoms nor a positive test for COVID-19 but has decided to discontinue treatment due to personal choice related to COVID-19 concerns.

Patients who discontinue study drug for reasons other than PD by RECIST version 1.1 should undergo scans for tumor assessment according to the original tumor assessment schedule (every 8 to 12 weeks [ $\pm$  1-week window (7 days)] from Cycle 1 Day 1) until any of the following occurs, whichever comes first:

- PD by RECIST version 1.1
- Initiation of new anticancer treatment
- Discontinuation from the study (death, withdrawal of consent, or loss to follow-up)

After discontinuation from study drug, all patients will have an EOT Visit. The EOT Visit should take place 30 days ( $\pm$  7 days) after the last study drug administration or before starting new anticancer treatment. If the patient begins another form of anticancer therapy before the end of the 30-day period, every effort will be made to complete all EOT assessments before commencing the new therapy. If there is an AE in need of monitoring beyond the EOT Visit, patients will be followed until resolution or confirmed stability of the AE. Long-term follow-up visits, to obtain survival information, after the EOT will be performed every 12 weeks ( $\pm$  7 days) until the endpoint of death, the patient is lost to follow-up, or for 24 months following the first dose of study drug of the last patient enrolled, whichever comes first.

Withdrawal from the study should be in a step-wise fashion. As mentioned above, patients may withdraw or be withdrawn from study drug. Any patient who withdraws or is withdrawn from study drug should be encouraged to complete all planned safety and follow-up assessments. If the patient wishes to withdraw from all study assessments, permission should be requested to contact the patient, a designated contact person, or the patient's primary care provider for long-term survival follow-up. If the patient does not wish any direct follow-up, permission should be requested to conduct periodic medical record review and/or contact the patient's medical care provider for long-term follow-up. If the patient withdraws from the study and also withdraws consent for disclosure of future information, no further evaluations should be performed, and no additional data should be collected. Where allowed by local regulations, public records may still be consulted for the patient's survival status.

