### 6.2.1 Milademetan Dose Modifications

## **6.3 Trabectedin Administration**

Trabectedin will be administered at 1.5 mg/m^2 BSA as a 24-hour IV infusion, every 3 weeks through a central venous line. Clinical laboratory assessments must be resulted and evaluated prior to administration of study drug on the day of administration.

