### **6.7.1 Screening Period/Baseline Assessments**

Patients may be screened anytime during the 21 days prior to randomization. Unless otherwise specified, baseline assessments may be done anytime following consent and prior to randomization. Patients who are determined not to meet eligibility criteria at any time prior to randomization will not be enrolled. The following will be assessed or measured at screening/baseline:

- Informed consent
- Eligibility (including tumor assessment)
- Medical/Disease history including all anticancer treatment
- Demographics
- Physical examination and vital signs, including height and weight
- ECOG
- ECG (12-lead) in triplicate

- Collect blood samples for laboratory assessments (see [Table 2](#) [milademetan arm] and [Table 5](#) [trabectedin arm]); ensure a serum pregnancy test is collected within 21 days of Cycle 1 Day 1 for WOCBP
- Patient-reported outcome questionnaire (EORTC QLQ-C30)
- Tumor tissue
  - Formalin-fixed paraffin embedded (FFPE) block from newly obtained biopsy or archival tissue of approximately 25 FFPE sections. Two sections will be used for eligibility confirmation after enrollment (enrollment is based on local pathology). The remaining 23 sections will be used for future genetic testing.

- In patients who provide consent to the optional procedure:
  - Tumor biopsy consisting of sufficient tissue to generate an FFPE block of approximately 25 sections. Refer to the study Laboratory Manual for details.
- Concomitant medications
  - Record all concomitant medications used after 21 days prior to Cycle 1 Day 1
  - Special attention should be accorded to medications that are known to cause prolongation of QTc or deplete potassium
- Baseline physical and radiographic tumor assessment
  - Perform physical examination and radiological assessments per RECIST version 1.1; include a computed tomography (CT) scan or magnetic resonance imaging (MRI) of the chest, abdomen, and pelvis, unless otherwise clinically indicated. The baseline radiographic tumor assessment is required within 28 days ( $\pm$  1 week window [7 days]) prior to the first dose of study drug.

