### 6.7.2 Treatment Period

See the Schedule of Events for the timing of procedures during the Treatment Period ([Table 1](#) [milademetan arm] and [Table 4](#) [trabectedin arm]). Blood samples will be collected at the time points indicated in [Table 2](#) (milademetan arm) and [Table 5](#) (trabectedin arm). If screening laboratory assessments were performed within 72 hours of Cycle 1 Day 1 dosing, these screening laboratory assessments can be used as Cycle 1 Day 1 safety laboratory assessments.

Physical and radiographic tumor assessments will be performed at the end of Week 8, Week 16, Week 24, and Week 32; and then every 12 weeks ( $\pm$  1 week [7 days]) until treatment discontinuation, and any other time during the study as clinically indicated. In accordance with RECIST version 1.1, response (PR and CR) must be confirmed by a subsequent tumor assessment at least 4 weeks after the initial observed response. The same imaging modality used for baseline imaging (i.e., CT or MRI) must be used for subsequent radiographic tumor

assessments. Any dose interruption after starting study treatment will not cause adjustment to the tumor assessment schedule. Additional tumor assessments may be performed as clinically indicated (e.g., if disease progression is suspected).

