#### **6.8.1 Prohibited Medications**

## 7. ASSESSMENT OF EFFICACY

Tumor assessments via imaging (CT scans or MRIs) will be performed by both the Investigator and a blinded central review committee; the evaluation of tumor response will be based on RECIST version 1.1. The primary efficacy objective is to compare PFS, as determined by BICR, between patients receiving milademetan versus trabectedin. However, the decision to discontinue study drug for disease progression will be determined locally by the Investigator.

Tumor response evaluations will be performed at screening; at the end of Week 8, Week 16, Week 24, and Week 32; and then every 12 weeks ( $\pm$  1 week [7 days]) while the patient remains on study drug, and any other time during the study as clinically indicated.

In accordance with RECIST version 1.1, response (PR and CR) must be confirmed by a subsequent tumor assessment at least 4 weeks after the initial observed response. The scheduling of subsequent tumor assessments may be adjusted based on the date of the most recent imaging. Investigators are instructed to ensure that original images (or high-quality copies) of all baseline and on-study scans are filed and available for transmission to the Sponsor (or designee) for central reading.

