#### **7.4. Efficacy Analyses**

#### **7.4.1. Progression Free Survival (PFS)**

Progression free survival (PFS) is defined as the time interval from the date of randomization until the first date on which progression (per RECIST v1.1) or death due to any cause, is documented, whichever comes first. Assessment of PFS will be performed for all patients at baseline, at the end of W8, W16, W24, W32, and then every 12 weeks ( $\pm$  1 week), regardless of treatment schedule modification (e.g., dose delay), until documented disease progression, initiation of new anticancer therapy, or discontinuation from the study (death, withdrawal of consent, or loss to follow-up). Subjects without documented progressive disease (PD) or death, including those who dropped out, will be censored at their last tumor assessment. Patients who did not have any tumor assessments after the screening visit will be censored on the randomization date.

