#### **7.4.3. Disease Control Rate (DCR)**

Disease control rate is the proportion of patients who achieve overall tumor response (confirmed CR or PR) or SD as assessed by RECIST 1.1 at least 16 (-1 week tumor assessment window) weeks from randomization.

[figure not shown]

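### PFS and DCR run from randomisation, but the only stated origin for follow-up scans is first dose, so unequal time to first dose would shift scan-dated progressions in one arm

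*Protocol*

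**What the plan says.** **Endpoint clock.** Protocol 4.3.1 has "PFS defined as the time from randomization to the earliest date of the first objective documentation of radiographic disease progression" by BICR, or death. SAP 4.1 and 7.4.1 use the same origin. SAP 7.4.3 counts disease control "at least 16 (-1 week tumor assessment window) weeks from randomization".

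**Scan clock.** Protocol 5.4 covers patients who stop drug for reasons other than progression. It keeps them on the original schedule, given as every 8 to 12 weeks with a "1-week window (7 days)] from Cycle 1 Day 1) until any of the following occurs". Protocol 6.7.1 also ties the baseline scan to dosing: within 28 days, with a "1 week window [7 days]) prior to the first dose of study drug". The synopsis, Protocol 6.7.2 and 7, and SAP 7.4.1 list Weeks 8, 16, 24, 32 and then every 12 weeks, but none of them says what Week 0 is.

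**Safeguards.** Protocol 6.7.2 states: "Any dose interruption after starting study treatment will not cause adjustment to the tumor assessment schedule". SAP 7.4.1 holds assessments regardless of changes to the treatment schedule, with dose delay as its example. Protocol 7, however, says: "The scheduling of subsequent tumor assessments may be adjusted based on the date of the most recent imaging".

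**Starting treatment.** Milademetan is an oral capsule. Trabectedin is given "as a 24-hour IV infusion, every 3 weeks through a central venous line". The visible text sets no explicit limit on the time from randomisation to first dose.

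**The concern.** A progression found on a scheduled scan carries the date of that scan. If scans are counted from first dose while PFS is counted from randomisation, a patient's time to first dose is added to every scan-dated progression time. An equal lag in both arms does little harm. An unequal lag offsets one arm's scan dates from the other's.

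The log-rank test depends on the order of events, and progressions cluster at the scheduled scans. A small systematic offset can therefore place one arm's cluster after the other's. The ±7-day window blurs this but does not remove it. A later trabectedin start would work against milademetan and cost power. A later milademetan start would favour milademetan.

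The two arms differ in what must be arranged before the first dose, and the trial is open-label with arm-specific preparation after assignment. An unequal lag is therefore plausible, though no document reports one.

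One gap needs no assumption about lags. SAP 7.4.1 says "Assessment of PFS will be performed for all patients at baseline" and at the listed weeks, the ITT population (SAP 5.1) includes everyone randomised, and SAP 7.2.1 tabulates patients randomised but not treated. Such a patient has no Cycle 1 Day 1 from which to count weeks.

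**Working it through.** **Inputs from the documents.** 105 PFS events; medians 3 months (trabectedin, stated as at most 3) and 6 months (milademetan); about 160 patients 1:1; about 12 months' accrual; scans at Weeks 8, 16, 24, 32 then every 12 weeks, ±7 days; censoring at the last tumour assessment (SAP 7.4.1).

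**Assumptions.** Alpha and the primary test are not visible, so I take log-rank at two-sided 0.05. Also assumed: exponential PFS, uniform accrual, 10% of events as deaths, and all times to first dose.

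**Benchmark.** With HR = 3/6 = 0.50, Schoenfeld power is Φ(√105/2 × ln 2 − 1.96) = Φ(3.55 − 1.96) = 94.4%. This does not confirm the plan's 105 events, because its alpha and power are not visible.

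**Simulation, scans counted from first dose.** Lags are exponential, with a mean of 2 days in the earlier arm and 3, 4, 5 or 7 days in the later arm. There were 4,000 to 12,000 runs per setting (Monte Carlo error 0.3-0.5 points on power, 0.2-0.3 on false wins).

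- Equal lags (2 and 2 days): power 93%, HR 0.51.
- Trabectedin later by a mean of 1, 2, 3 or 5 days: power 91%, 90%, 89%, 86%; HR 0.52 to 0.54. With no true effect and both medians 4.2 months, the HR drifts to 1.02-1.07. With both at 3 months, the 5-day gap gives about 1.09.
- Milademetan later by a mean of 3 or 5 days, no true effect: false wins for milademetan 4.4-5.2% or 5.6-6.7%, against 2.5%. The ranges span the two null medians.

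**Sensitivity.**

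- 25% of progressions found at unscheduled scans, 5-day mean gap: power 89%, or false wins 4.1-5.1% in the reverse direction.
- Gamma lags (shape 2), means 7 and 2 days: power 85%; reversed, false wins 6.6-8.4%.
- Upper case, a constant 7-day trabectedin delay: power 77%, or 83% with 25% unscheduled detection.
- Censoring at the data cut instead of the last assessment weakens the effect: a fixed 7-day trabectedin delay then gives power of about 85%.

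**Scans counted from randomisation.** With 5-day or 7-day gaps, power is 92-93%, false wins 2.2-2.7% and null HR 1.00.

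**DCR.** The share progression-free at the Week 16 scan is 2^(−t/median), with medians of 91.3 and 182.6 days. Moving the scan from day 112 to day 119 changes it as follows:

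- Trabectedin: 2^(−112/91.3) = 43% to 2^(−119/91.3) = 41%.
- Milademetan: 2^(−112/182.6) = 65% to 2^(−119/182.6) = 64%.

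In the delayed arm DCR falls while PFS appears longer.

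**The case against.** **The anchor is thin.** It is a parenthesis in a withdrawal section, about patients already off drug, with the schedule loosely paraphrased. That is fair, but the sentence calls it the original schedule, so it describes the calendar those patients were already on.

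**Other passages point to randomisation.** SAP 7.4.3 applies the scan window on the randomisation clock, and the dose-delay clause in SAP 7.4.1 could be read to cover a late first dose. The first sets an endpoint threshold, not a scan calendar. The second names no Week 0. Neither supplies a competing origin, though both show that the intent may have been randomisation.

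**Much is not visible.** The schedules of events, the BICR section, the PFS analysis and sensitivity sections and the protocol's statistics section are missing from this copy. An anchor, a dosing limit or a scan-timing sensitivity analysis may be there. This stands, and it limits confidence. If the tables do use randomisation, Protocol 5.4 contradicts them and still needs the edit.

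**The lag is loosely bounded.** A baseline scan done before randomisation and within 28 + 7 = 35 days of first dose caps the lag at about 35 days. That is too wide to help.

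**The effect is hypothetical.** The one visible asymmetry, oral capsule against central-line infusion, suggests a later trabectedin start, which is conservative for milademetan. At a mean gap of 1 day the loss of power is about 2 points. If half of progressions are found at unscheduled scans, a 5-day gap leaves power at 90%. All of this stands. The false-win figures need milademetan to start later, and the documents give no reason to expect that.

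**Never-dosed patients.** SAP 7.4.1 censors at randomisation those with no post-screening scan. That settles their analysis if unscanned, but not when they should be scanned.

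**Conclusion.** The mismatch is real in the visible text: endpoints run from randomisation, and the only stated origin for follow-up scans is first dose. Whether it biases anything depends on a between-arm difference in time to first dose that the documents do not report.

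Under the assumed mean gaps of 1 to 5 days, the cost is about 2 to 7 points of power if trabectedin starts later. If milademetan starts later by 3 to 5 days, false wins rise to roughly twice to two and a half times the nominal 2.5%. DCR is barely affected. These figures rest on exponential PFS, log-rank at two-sided 0.05, censoring at the last assessment and mostly scheduled detection. Deaths and unscheduled scans do not move with the schedule, so more of either shrinks the effect.

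The point is worth acting on because the remedy is simple and protects the primary endpoint of an open-label registration trial. It does not show that the design is flawed. Confidence is medium because the schedule tables are not shown.

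**What to change.** 1. In Protocol 5.4, count the tumour assessment schedule from randomisation in place of Cycle 1 Day 1.
2. State that same origin for the Week 8, 16, 24, 32 and every-12-week assessments in both arms: in the synopsis, Protocol 6.7.2 and 7, SAP 7.4.1 and the schedules of events. Say that it also applies to patients randomised but never dosed.
3. Add a summary of time from randomisation to first dose by arm to the SAP's planned tables.
4. For consistency only, reconcile the sentence in Protocol 7 on re-timing later scans with the fixed calendar in Protocol 6.7.2 and SAP 7.4.1. Its effect on the HR is about 0.01 or less.

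The cost is protocol wording, a site instruction and one extra table. The number of scans does not change. The one drawback is that the first scan may fall a few days sooner after first dose.
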